9.1 Antitumor Effect- Solid Tumors

For the purposes of this study, participants will undergo radiographic reevaluation at baseline, every 24 weeks from Cycle 46 on, and at their off-study evaluation. In addition to a baseline scan, confirmatory scans may also be obtained 4-6 weeks following initial documentation of objective response. Response and progression will be evaluated using consensus guidelines of RECIST 1.1 and PCWG2^{14,15}.

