5.1 Pre-treatment Criteria

All subjects must have the following within 21 days prior to start of protocol therapy:

- History and physical examination
- ECOG performance status
- Vital signs (including blood pressure, body temperature, heart rate and respiratory rate)
- Availability and review of prior medical records
- Concomitant medications
- Adverse event assessments
- Serum PSA
- Serum testosterone
- Complete blood count
- Serum chemistries
- Thyroid function test (TSH only)
- Coagulation studies
- Urinalysis (urine protein only)
- Electrocardiogram
- Chest x-ray

- Bone scan (repeat scans every 3 cycles up to Cycle 46 then repeat every 6 cycles)
- Abdomen/pelvic CT scan (repeat scans every 3 cycles up to Cycle 46 then repeat every 6 cycles)

Based on these studies, eligibility must be confirmed according to the guidelines in Section 3 above.

5.1.1 Day 1 of Cycle 1

The following data should be collected on Cycle 1 Day 1 (+/- 3 days):

- History and physical exam
- Concomitant medications
- Vital signs (including blood pressure, body temperature, heart rate and respiratory rate)
- ECOG performance status
- Complete blood count
- Serum chemistries
- Urinalysis (urine protein only)
- Adverse event assessments

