5.1.2 Day 1 of Every 3rd Cycle

The following data should be collected on Day 1 (+/- 3 days) of every 3rd cycle (see Schedule of Events):

- History and physical examination
- ECOG performance status
- Vital signs (including blood pressure, body temperature, heart rate and respiratory rate)
- Complete blood count
- Serum chemistries
- Thyroid function test (TSH only; every odd number Cycle beyond Cycle 1 up to Cycle 46 and then every 3rd Cycle)
- Urinalysis (urine protein only)
- Serum PSA
- Concomitant medications
- Adverse event assessments
- Study drug diary

[Note: If ECOG performance status, physical examination, hematology, serum chemistry, coagulation studies, and urinalysis were measured/performed within 7 days prior to Cycle 1, Day 1, they need not be repeated at that visit.]

If any treatment-related grade ≥ 3 non-hematologic or grade ≥ 4 hematologic adverse events are observed, then treatment should be held until resolution of the event(s) to \leq grade 2. The attribution of the events to either or both of the study drugs will be at the discretion of the treating physician, and only the responsible drug should be held. Doses that are held will not be

made up, and the cycle number and cycle day will continue chronologically regardless of whether treatment is held.

If either study drug is held for \geq 4 weeks, regardless of cause, then the patient should be removed from study treatment.

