5.1.3 Off Study Visit

The following data should be collected during the off study visit:

- History and physical exam
- Concomitant medications
- Vital signs (including blood pressure, body temperature, heart rate and respiratory rate)
- ECOG performance status
- Serum PSA
- Complete blood count
- Serum chemistries
- Urinalysis (protein only)
- Bone scan and abdominal/pelvic CT scans (performed if an assessment has not been performed within the prior 6 weeks)
- Adverse event assessments

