8. STUDY CALENDAR

Baseline evaluations are to be conducted within 3 weeks prior to start of protocol therapy. Subsequent evaluations should be carried out on Day 1 of subsequent cycles (+/- 3 days) every 12 weeks from Cycle 46 on. Radiographic evaluations including bone and abdominal/pelvic CT scans should be conducted at baseline and every 24 weeks from Cycle 46 on.

| | Pre- Study | Cycle 1 Day 1 ^x | Cycle 2 to Cycle 45, Day 1 ^x | Day 1 Cycles ≥ 46, Every 12 Weeks ^x | Off Study ^b |
|---|---------------|-------------------------------|---|--|------------------------|
| Treatment Schedule: | | | | | |
| Tivozanib | | X (days 1-21) | X (days 1-21) | X (days 1-21) | |
| Enzalutamide | | X (Days 1-28) | X (days 1-28) | X (days 1-28) | |
| Informed consent | X | | | | |
| Demographics | X | | | | |
| Medical/Interval history | X | X | X | X | X |
| Concurrent meds | X | X | X | X | X |
| Physical exam | X | X | X | X | X |
| Vital signs/ BP | X | X | X | X | X |
| Performance status | X | X | X | X | X |
| Serum PSA | X | | X | X | X |
| PT, PT/INR, and PTT | X | | | | |
| CBC w/diff, plts | X | X | X | X | X |
| Serum chemistry ^a | X | X | X | X | X |
| Serum testosterone | X | | | | |
| Thyroid Function (TSH only) | X | | X (odd cycles) | X | |
| Urinalysis (urine protein only) | X | X | X | X | X |
| Chest xray | X | | as clinicall | y indicated | |
| Bone scan and abdominal/pelvis CT scans | X | Rep | Repeat scans every 24 weeks | | X ^c |
| EKG | X | | | | |
| Adverse Event Evaluation | X | Х | | | -X |
| Survival follow-up | | | | | X ^d |

x: ± 3 days for treatment or assessment requirement

MEASUREMENT OF EFFECT

a: Sodium, potassium, chloride, BUN, creatinine, glucose, albumin, total protein, total bilirubin, alkaline phosphatase, SGOT [AST], SGPT [ALT]

b: Off-study evaluation should occur within 30 days after the last dose of study treatment c: Post-treatment scans will be performed if an assessment has not been performed within the prior 6 weeks

d: Follow for survival information every 3 months until death, up to 2 years after discontinuing therapy, or patient lost to follow-up

The primary endpoint of the study is progression free survival (PFS). Secondary clinical endpoints will include safety, overall survival, time to PSA progression, PSA response rate and objective response rate.

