The consensus guidelines of RECIST 1.1 and PCWG2 have been taken into consideration for the determination of radiographic disease progression {Eisenhauer, 2009 #274;Scher, 2008 #261}. Disease progression will consist of confirmed radiographic disease progression, death due to disease, or clinical disease progression. Radiographic disease progression is defined either by RECIST 1.1 for soft tissue disease, or by the appearance of two or more new bone lesions on bone scan (PCWG2).

Confirmation of progression by RECIST requires redemonstration of soft tissue progression by a scan of the same modality a minimum of 4 weeks later.

If the initial restaging bone scan showed progression by PCWG2 (two or more bone lesions), then confirmation of progression by PCWG2 on the next bone scan requires two or more new bone lesions compared to the first bone scan showing progression. Additionally, at least two of the new lesions from the first scan must still be present.

If progression by PCWG2 occurs not on the initial bone scan but on subsequent bone scans, then confirmation of progression requires either persistence or increase in number of lesions compared to the first bone scan showing progression.

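### The imaging schedule behind the primary PFS endpoint contradicts itself: Section 9.1 and the Section 8 prose schedule no routine scan before Cycle 46 (month 41.4), while Section 5.1 asks for one every 3 cycles

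*Combined protocol and SAP*

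**What the plan says.** Three current sections of the protocol state when scans are done.

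- **Section 9.1** (Antitumor Effect): "participants will undergo radiographic reevaluation at baseline, every 24 weeks from Cycle 46 on, and at their off-study evaluation".
- **Section 8** (Study Calendar, prose): "Radiographic evaluations including bone and abdominal/pelvic CT scans should be conducted at baseline and every 24 weeks from Cycle 46 on".
- **Section 5.1** (Pre-treatment Criteria): "Bone scan (repeat scans every 3 cycles up to Cycle 46 then repeat every 6 cycles", and for CT "Abdomen/pelvic CT scan (repeat scans every 3 cycles up to Cycle 46 then repeat every 6 cycles". The repeat interval stands in a bracket within a list of screening tests.

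Section 5.1.2, the on-treatment visit list ("The following data should be collected on Day 1 (+/- 3 days) of every 3rd cycle (see Schedule of Events"), names no scan. Section 5.1.3 adds an off-study scan with a condition: "Bone scan and abdominal/pelvic CT scans (performed if an assessment has not been performed within the prior 6 weeks".

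On the endpoint, the Measurement of Effect text that follows the calendar states: "Disease progression will consist of confirmed radiographic disease progression, death due to disease, or clinical disease progression". Soft-tissue progression must be shown again by the same modality at least 4 weeks later. Bone progression is confirmed on the next bone scan, and the rule depends on whether it first appeared on the first restaging scan or on a later one. Section 9.1.4 censors patients without progression at their last disease evaluation. Section 14.4 places the first on-study disease assessment after 2 cycles in one sentence and after 3 cycles in 14.4.2.

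**The concern.** Section 9.1 is where a reader looks for the assessment schedule, and it reads as the study's full list of radiographic evaluations. Followed literally, it gives a patient a baseline scan and then nothing routine until Cycle 46. A site that works from the bracket in Section 5.1 would scan every 12 weeks. The two schedules coincide only from Cycle 46 on, where 6 cycles equal 24 weeks.

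The date of radiographic progression is the date of a scan, so sites that follow different sections would date the same disease course differently. Under Section 9.1 there is no scheduled on-treatment scan before Cycle 46 to detect progression, and no scheduled next bone scan on which to confirm it. PFS events would then come only from clinical progression, death, and off-study or unscheduled scans. The primary test is planned on 20 PFS events (Section 14.1).

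**Working it through.** **Inputs.** A cycle is 4 weeks (Section 5.2.1), and cycle numbering runs on by the calendar even when treatment is held (Section 5.1.2). Accrual takes 21 months, with 6 months of further follow-up (Section 14.2). The median PFS is 14 months under the null and 22.4 months under the alternative, with 38 patients, 20 events and one-sided alpha 10% (Section 14.1). A month is taken as 30.4375 days.

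**The plan's own figures.** The hazards are ln 2 / 14 = 0.0495 and ln 2 / 22.4 = 0.0309 per month, with ratio 0.625, as stated. For the exact one-sample exponential test with 20 events, power = P(χ² on 40 df > 0.625 × its 90th percentile) = 79.9%. The stated 80% reproduces, so the design model can be used for the timing.

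**When the first routine repeat scan falls under Section 9.1.**
- Cycle 46 Day 1 = 45 × 28 = 1,260 days = 180 weeks; 1,260 / 30.4375 = 41.4 months.
- If the first scan comes 24 weeks after Cycle 46 Day 1: (1,260 + 168) / 30.4375 = 46.9 months. So 41.4 is the earliest reading.
- Planned study: 21 + 6 = 27 months = 821.8 days. The gap is 41.4 − 27 = 14.4 months.
- First patient at month 27: 821.8 / 28 = 29.35 cycles completed, so in Cycle 30.
- Last patient, 6 months (182.6 days) on study: 182.6 / 28 = 6.52, so in Cycle 7.

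Nobody reaches Cycle 46 within the plan.

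**Share of patients with a PFS event before month 41.4**, by 1 − exp(−λt):
- Null: 1 − exp(−0.0495 × 41.4) = 0.871, or 33.1 of 38.
- Alternative: 1 − exp(−0.0309 × 41.4) = 0.722, or 27.4 of 38.

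**Scheduled repeat scans by month 27, if still on treatment.**

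| Reading | First patient enrolled | Last patient enrolled |
|---|---|---|
| Section 5.1, every 84 days | floor(821.8 / 84) = 9 | floor(182.6 / 84) = 2 |
| Section 5.1, on Day 1 of Cycles 3, 6, 9 … (days 56, 140, 224 …) | 10 | 2 |
| Section 9.1, literal | 0 (1,260 > 821.8) | 0 |

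**Text that presupposes early scans.** The progression definition relies on a first restaging bone scan and a following one. Section 12.1 ties a form deadline to the cycle in which response is evaluated. Section 14.3 estimates an objective response rate. Section 14.4 expects an assessment after 2 or 3 cycles. None of these fits a first routine scan at Cycle 46.

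**The case against.** The strongest reply is that Sections 8 and 9.1 are silent on Cycles 1 to 45; they do not forbid scans, and Section 5.1 gives the only explicit interval. The neighbouring Section 8 sentence on visits, "Subsequent evaluations should be carried out on Day 1 of subsequent cycles (+/- 3 days) every 12 weeks from Cycle 46 on", has the same wording, and read literally it would drop routine visits before Cycle 46 as well. Yet the calendar has a column for Cycles 2 to 45 marked for PSA, blood tests and examination. The likeliest explanation is an edit that kept only the later phase of a two-phase schedule. This stands as the cause, but it does not remove the conflict, because Section 9.1 still reads as a complete list.

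Two points limit the evidence. The calendar's scan row is broken in the copy reviewed, so it is not used here; the intact calendar should be checked, since it may state an interval for Cycles 1 to 45. Section 5.1.2 names no scan for any cycle, so its silence does not itself show a gap.

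It is also fair that 87% and 72% restate the design medians at month 41.4 and do not count lost or misdated events. Clinical progression and death still count, and off-study scans remain. Those scans, however, come after a patient has stopped treatment, and only survival follow-up is scheduled after that visit (Sections 5.5 and 8). Progression first seen there therefore has no scheduled confirmation scan.

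**Conclusion.** The concern holds and must be fixed. As written, the protocol carries two incompatible imaging schedules for the primary endpoint. The one in the antitumor-effect section provides no routine on-treatment scan until at least 14.4 months after the planned end of the study. The difference by month 27 is 9 repeat scans against 0 for the first patient and 2 against 0 for the last.

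These figures assume 30.4375-day months, Cycle 1 Day 1 close to registration (from which PFS is counted), patients still on treatment, and, for the event shares, the protocol's exponential model. No direction or size of bias in the PFS test is claimed; that would depend on which section each site follows.

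**What to change.** Reconcile Sections 5.1, 5.1.2, 8 (prose and calendar) and 9.1 to one imaging schedule that covers Cycles 1 to 45 as well as Cycle 46 on, and state when the confirmation scan is done. The sponsor must say which schedule is intended; this review does not choose the interval.

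Then bring the two statements in Section 14.4 into line with it. After 2 cycles fits a first repeat scan on Cycle 3 Day 1 (day 56); after 3 cycles fits one after three completed cycles (day 84). As a minor clarification, say in Sections 9.1.4 and 14.1 whether the last disease evaluation used for censoring is a scan or a visit.

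The cost is protocol wording. If Section 5.1 is the intended schedule, no routine scans are added beyond those it already specifies, and confirmation scans are already required by the progression definition. If another schedule is intended, the scan count will differ.

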9.1.1 Definitions

Evaluable for toxicity. All participants who receive at least one dose of study treatment will be evaluable for toxicity from the time of their first treatment.

Evaluable for objective response. Only those participants who have received at least one cycle of therapy, and have had their disease re-evaluated will be considered evaluable for response. These participants will have their response classified according to the definitions stated below. (Note: Participants who exhibit objective disease progression or die prior to the end of cycle 1 will also be considered evaluable.)

9.1.2 Disease Parameters by RECIST 1.1

Measurable disease. Measurable disease is a lesion that can be accurately measured in at least one dimension with longest diameter >20 millimeters (mm)

using conventional techniques (CT, MRI, x-ray) or >10 mm with spiral CT scan. Measurable lesions must be at least 2 times the slice thickness in mm. All tumor measurements must be recorded in millimeters (or decimal fractions of centimeters).

A lesion in a previously irradiated area is not eligible for measurable disease unless there is objective evidence of progression of the lesion prior to study enrollment. Lesions in previously irradiated areas must be clearly identified as such.

Malignant lymph nodes. To be considered pathologically enlarged and measurable, a lymph node must be ≥ 15 mm in short axis when assessed by CT scan (CT scan slice thickness recommended to be no greater than 5 mm). At baseline and in follow-up, only the short axis will be measured and followed.

Non-measurable disease. All other lesions (or sites of disease), including small lesions (longest diameter <10 mm or pathological lymph nodes with ≥ 10 to <15 mm short axis, are considered non-measurable disease. Bone lesions, leptomeningeal disease, ascites, pleural/pericardial effusions, and cystic lesions are all considered non-measurable.

Target lesions. All measurable lesions up to a maximum of 2 lesions per organ and 5 lesions in total, representative of all involved organs, should be identified as target lesions and recorded and measured at baseline. Lesions must be accurately measured in 1 dimension with a minimum size of 10 mm by CT scan. Nodes must have a short axis \geq 15 mm. The short axis should be included in the sum of the lesions in the calculation of response. Nodes that shrink to < 10 mm are considered normal. Target lesions should be selected on the basis of their size, be representative of all the involved organs, and should be lesions that can be followed with reproducible repeated measurements.

Lytic bone lesions or mixed lytic-blastic lesions, with identifiable soft tissue components, that can be evaluated by cross sectional imaging techniques such as CT or MRI can be considered target lesions if the soft tissue component meets the definition of measurability as defined above.

9.1.3 Response Criteria

9.1.3.1 Evaluation of Target Lesions

Complete Response (CR): Disappearance of all target lesions. Any pathological lymph node must have reduction in short axis to < 10 mm.

Partial Response (PR): At least a 30% decrease in the sum of the diameters of target lesions, taking as reference the baseline sum diameters.

Progressive Disease (PD): At least a 20% increase in the sum of the diameters of target lesions, taking as reference the smallest sum on study with at least a 5 mm absolute increase in the sum of all lesions. The appearance of one or more new lesions* denotes disease progression.

Stable Disease (SD): Neither sufficient shrinkage to qualify for PR nor sufficient increase to qualify for PD, taking as reference the smallest sum diameters while on study.

Unknown (UN): Assessment of target lesions cannot be made due to insufficient or unevaluable data.

*Definition of New Lesion: The finding of a new lesion should be unequivocal (i.e. not due to difference in scanning technique, imaging modality, or findings thought to represent something other than tumor (ex: new bone lesions may be healing or flare of pre-existing lesions). However, a lesion identified on a follow-up scan in an anatomical location that was not scanned at baseline is considered new and will indicate PD. If a new lesion is equivocal (because of small size, etc.), follow-up evaluation will clarify if it truly represents new disease and if PD is confirmed, progression should be declared using the date of the initial scan on which the lesion was discovered.

9.1.3.2 Evaluation of Non-Target Lesions

Complete Response (CR): Disappearance of all non-target lesions and normalization of tumor marker level. All lymph nodes must be non-pathological in size (< 10 mm short axis).

Incomplete Response/Stable Disease (SD): Persistence of one or more non-target lesions and/or maintenance of tumor marker level above the normal limits.

Progressive Disease (PD): Appearance of one or more new lesions* (new lesions must be > slice thickness) and/or unequivocal progression of existing non-target lesions.

Unknown (UN): Assessment of non-target lesions cannot be made due to insufficient or unevaluable data. In this case, a concise explanation must be given.

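### Section 9.1.3 makes one new lesion progressive disease without excepting bone: this conflicts with Section 9 for objective response and leaves room for inconsistent PFS events

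*Combined protocol and SAP*

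**What the plan says.** **Study definition of progression (opening of Section 9, Measurement of Effect).** "Disease progression will consist of confirmed radiographic disease progression, death due to disease, or clinical disease progression". The radiographic part follows: "Radiographic disease progression is defined either by RECIST 1.1 for soft tissue disease, or by the appearance of two or more new bone lesions". That bone rule refers to findings on a bone scan and names PCWG2 as its source. Soft-tissue progression must be shown again on the same modality at least 4 weeks later. Bone progression has its own confirmation rule. If the first restaging scan shows it, the next scan must show at least two further new lesions, and at least two of the earlier ones must still be present. On later scans, persistence or an increase is enough.

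**Response criteria (Section 9.1.3).** For target lesions, 9.1.3.1 says: "The appearance of one or more new lesions* denotes disease progression". For non-target lesions, 9.1.3.2 defines progressive disease as "Appearance of one or more new lesions* (new lesions must be > slice thickness) and/or unequivocal progression of existing non-target lesions".

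**Where bone sits.** Section 9.1.2 says: "Bone lesions, leptomeningeal disease, ascites, pleural/pericardial effusions, and cystic lesions are all considered non-measurable". Its exception is a lytic or mixed lesion with a measurable soft-tissue component. The new-lesion footnote in 9.1.3.1 mentions bone only as an example of a doubtful finding: "new bone lesions may be healing or flare of pre-existing lesions". If an equivocal lesion is later confirmed, the footnote dates progression to the scan that first showed it.

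**Which rule applies.** Section 9.1 says: "Response and progression will be evaluated using consensus guidelines of RECIST 1.1 and PCWG2". It gives no order of precedence. Sections 9.1.4 and 14.1 count radiographic or clinical progression, or death, as the PFS event, and neither refers back to the definition at the start of Section 9.

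**The concern.** Bone is where the two sets of rules diverge. Section 9.1.3 needs one new lesion of any kind, or unequivocal worsening of an existing non-target lesion. Section 9 needs two new bone-scan lesions and counts only new ones. Bone lesions without a measurable soft-tissue component cannot be target lesions, so by default they fall under the non-target rule. That rule does not exempt them.

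For the response rate, the choice of section decides whether some men are responders. For PFS, the stake is whether sites apply one event definition throughout. The trial compares a single arm with a fixed 14-month median on 20 events, so a few events recorded early or wrongly can move the result.

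**Working it through.** **1. One case, both rules.** Take a man whose nodal target lesions shrink by 40% and who has one unequivocal new bone lesion on restaging.

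| Question | Section 9.1.3 | Opening of Section 9 |
|---|---|---|
| Target lesions | Partial response (at least a 30% decrease) | RECIST 1.1 applies to soft tissue: no progression |
| One new bone lesion | Progressive disease; the footnote spares only healing or flare | Not progression: two or more needed |
| An existing bone lesion clearly worse | Can be progressive disease (non-target rule) | Not counted: only new lesions count |
| Bone lesion seen only on CT | Within the wording; the slice-thickness condition fits CT | Not addressed: the rule names bone scan |

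For response, Section 9.1 invokes both guidelines and does not say which governs bone, so the conflict stays open.

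**2. The same man for PFS.** Sections 9.1.4 and 14.1 count radiographic or clinical progression. The opening of Section 9 defines radiographic progression, and one new bone lesion does not meet it. Nor can that lesion satisfy the soft-tissue confirmation rule, because it is not soft-tissue progression. Read strictly, it is not a radiographic PFS event. A risk remains because 9.1.3.1 equates a new lesion with disease progression and its footnote assigns a progression date, while the PFS sections point to neither rule.

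**3. The plan's power figure (Section 14.1).** Inputs: medians 14 and 22.4 months, 20 events, one-sided 10%, one-sample exponential test.
- Hazards: ln 2/14 = 0.0495; ln 2/22.4 = 0.0309; ratio 0.625.
- With 20 events, 2 × hazard × total follow-up time follows a chi-square distribution with 40 degrees of freedom. Its 0.90 quantile is 51.81.
- Critical total time: 51.81/(2 × 0.0495) = 523 months, an observed median of (523/20) × ln 2 = 18.1 months.
- Power: P(chi-square(40) > 0.625 × 51.81 = 32.38) = 79.9%. The stated 80% reproduces.

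**4. Illustration of sensitivity.** Simulation of 38 men, uniform accrual over 21 months, exponential PFS, test at the 20th event, 20,000 trials per scenario. One scan interval is taken as 12 weeks (three 4-week cycles, Section 5.1), or 2.76 months. The percentages of men are assumptions; the documents give none.

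| Assumed effect of counting single bone lesions | Power | Type I error |
|---|---|---|
| None | 0.80 | 0.10 |
| 30% of men called one scan earlier | 0.73 | 0.063 |
| 5% of men given an event at the first scan who would otherwise have continued | 0.66 | 0.052 |
| 10% of men likewise | 0.50 | 0.027 |

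A second route multiplies the PFS hazard by f and keeps the 14-month null. Power is P(chi-square(40) > 32.38 × f).
- f = 1.05: threshold 34.00, power 73.6%, apparent median 22.4/1.05 = 21.3 months.
- f = 1.10: threshold 35.62, power 66.8%, apparent median 20.4 months.
- f = 1.20: threshold 38.85, power 52.2%, apparent median 18.7 months.

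Every non-zero scenario requires assessors to apply 9.1.3 to bone in spite of Section 9.

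**The case against.** The strongest reply is that the study already has one explicit definition of disease progression, in the opening of Section 9, and that it limits RECIST 1.1 to soft tissue. Section 9.1.3 is headed as response criteria and follows the RECIST disease parameters, so it can be read as supplying the RECIST categories that Section 9 applies to soft tissue. For PFS this reply stands.

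A reader might infer four stronger points, none of which the documents support:
- **That a man with one new bone lesion is both progressed and not progressed for primary PFS.** Section 9 defines the radiographic event and excludes him.
- **That confirmation offers no protection because the lesion is simply seen again.** Confirmation under RECIST concerns soft tissue, and the bone route starts at two new lesions.
- **That treatment necessarily stops.** Section 5.4 says only disease progression and does not point to 9.1.3.
- **That mixed rules make the result uninterpretable against the null.** In the scenarios above, type I error falls below 0.10, so the bias has a known, conservative direction.

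The slice-thickness condition in 9.1.3.2 also fits CT better than bone scan, so that rule's clearest clash concerns bone lesions seen on CT. The one-lesion sentence in 9.1.3.1 carries no such condition.

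For response the reply does not settle the matter. Section 9.1.1 says response is classified by the definitions that follow it, which favours 9.1.3, while Section 9.1 applies both guidelines to response and progression together. Following 9.1.3 for response and Section 9 for PFS would give the same man progressive disease for one endpoint and no progression for the other, and no text says that this is intended.

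**Conclusion.** The point holds in two parts of different strength. For objective response, a secondary endpoint, the one-lesion rule in 9.1.3 and the two-lesion bone rule in Section 9 ("by the appearance of two or more new bone lesions on bone scan (PCWG2") conflict, and nothing says which governs. For primary PFS, Section 9 read strictly governs; what remains is a risk that sites record events inconsistently, because the PFS sections do not cite it.

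The size of any effect cannot be derived from the documents. The losses from 80% power to 73%, 66% or 50% rest on assumed frequencies and on assessors setting Section 9 aside. They show that a 20-event single-arm test is sensitive to a few reclassified men and do not estimate the actual loss. On the same assumptions the danger is missing a real improvement, not claiming a false one. This is a textual correction to make before analysis, not a fault in the sample-size calculation, which reproduces.

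**What to change.** - Add to 9.1.3.1 and 9.1.3.2: *For the PFS and objective response endpoints, new or worsening bone lesions, on bone scan or CT, are assessed only by the bone-scan rule at the start of Section 9, except for a soft-tissue component that meets the target-lesion definition in 9.1.2.*
- Cite the Section 9 definition of disease progression in 9.1.4 and 14.1.
- Check completed response assessment forms against the clarified rule before analysis.
- Reconcile the meaning of disease progression in Section 5.4 with these passages. No treatment-stopping rule is proposed here.

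The cost is a short amendment and a review of existing forms. The downside is that a few assessments may be reclassified.
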